# **Exploratory Objectives:**

- 1) To evaluate the intraclass correlation (reliability) of hand-held POCUS for the assessment of second and third trimester fetal biometry
- 2) To assess the validity of hand-held POCUS in patients with different antenatal risk factors (SGA, Diabetes, and RFM)
- 3) To examine the efficiency of hand-held POCUS for second and third trimester assessment of fetal biometry
- 4) To determine the minimum sufficient sample size to detect a difference in measurements taken with

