#### **POCUS versus SUM**

#### 5.2. Outcome

The primary outcomes will be the acceptability and feasibility of point-of-care ultrasound to patients. This will be assessed as:

- 1) The number of patients approached who agree to participate (objective 1)
- 2) The response rate to the questionnaire (objectives 2 and 3)
- 3) The number of patients willing to undergo POCUS scans in the future as determined by the questionnaire responses (objective 2)
- 4) The number of unblinding episodes that occur (objective 4)

The exploratory outcomes will investigate the reliability and validity of the point-of-care ultrasound device. This will be assessed as:

- 1) For categorical data, Kappa coefficients demonstrating 90% agreement or greater (objectives 1 and 2)
- 2) For numerical data, ICC 0.9 or greater (objectives 1 and 2)
- 3) For continuous data (fetal biometric measurements), high level of agreement with Bland Altman, defined as ≥95% of the differences between the two measurement methods fall within the clinically acceptable range of ±3 to ±7 mm, depending on gestational age (objectives 1 and 2)
- 4) The difference in the mean time taken to perform each type of scan (POCUS and SUM) (objective 3)
- 5) The number of patients in whom fetal assessment could not be performed (objective 2)
- 6) Data from the feasibility study will inform the sample size calculation for the full randomized controlled trial by providing estimates of outcome variability, effect size, and recruitment parameters necessary for a power analysis (objective 4)

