#### 10. STATISTICS AND DATA ANALYSIS

### 10.1 Sampling

All pregnant patients attending Liverpool Women's Hospital Trust (diabetes antenatal clinic, fetal medicine unit growth clinic, maternity assessment unit with reduced fetal movements, admitted in antenatal ward with reduced fetal movements) will be considered to take part in this study.

As this is an exploratory study and no hypothesis testing is planned a formal sample size calculation has not been performed.

We will aim to include 60 patients per cohort. There will be three cohorts, so the total number of patients will be 180, and the number of scans performed 360. The sample size estimation was determined by the study team including the statistician because this is an exploratory study with a binary primary outcome (acceptable vs non-acceptable). A review of feasibility studies by Totton et al. (22) evaluated three studies of sample size estimations. The most recent of these studies was by Teare et al. (23), who recommend 60 participants per arm for feasibility studies with binary outcomes. 60 participants per cohort will generate sufficient results for feasibility and acceptability to achieve the proposed outcomes.

This sample size will also provide sufficient data for analysis of the secondary outcomes. As these are concerned with the level of agreement between the two ultrasound modalities, we will use Bland-Altman limits of agreement. Studies using this method rarely include sample size calculations, with an average sample size of 65.(24) The overall assessment of the devices from the combined three groups will involve a total sample of 180 paired scans.

Diabetes: The Diabetes antenatal clinic at LWH runs once a week on Tuesdays and sees between 20-40 patients per week. During a six-month period, this will equate to around 750 patients.

SGA: The Growth clinics at LWH run twice a week on Mondays and Thursdays and see roughly six patients per clinic. During a six-month period, this will equate to around 300 patients.

RFM: Patients present with RFM regularly to MAU at LWH. Around four patients per day will present. In a six-month period, this will equate to around 700 patients. The PI will aim to recruit from this clinical area weekly on Fridays.

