### 10.2 Data Analysis

### Data analysis and statistical analysis plan

Data arising from the questionnaires will be analysed in Microsoft Excel and will be reported using descriptive summary statistics, mean, medians, and counts (i.e. "54% of participants were satisfied with the POCUS scan").

Acceptability will be assessed using descriptive summary statistics, mean, medians, counts, and corresponding measures of variability.

Data will be analysed using SPSS (Statistical Package for the Social Sciences, IBM, Armonk NY).

The statistical methods have been chosen in collaboration with and at the advice of a University of Liverpool statistician ([name]) to ascertain agreement between the two methods of scanning (POCUS and SUM), and to enable appropriate statistical analysis of the proposed sample. Within each group we will use interclass correlation coefficients (ICC) and Spearman correlation coefficients (SCC) to check how closely the two methods agree by looking at the agreement between the paired measurements. Intraclass correlation coefficients measure how similar the measurements from the two methods are, indicating reliability or consistency for continuous variables. As the ICC approaches 1 (0.9 or greater), the greater the level of agreement. For this study, an ICC of 0.9 or greater will be considered a high level of agreement and indicate

increased reliability of the Vscan device.

To assess for difference in the scan duration, the mean scan time, median and interquartile ranges will be used. We will examine for correlation between the continuous variables of BMI and scan time with both POCUS and standard ultrasound. Calculation of a correlation coefficient will be performed with Spearman's correlation test.

Kappa coefficients measure agreement for categorical outcomes, such as assessments of fetal presentation or amniotic fluid levels. Values  $\leq 0$  indicate no agreement, 0.01–0.20 as none to slight, 0.21–0.40 as fair, 0.41–0.60 as moderate, 0.61–0.80 as substantial, and 0.81–1.00 as almost perfect agreement. These methods will be used to check for similarity within the methods (POCUS or SUM). This will ensure the measurements taken by the methods themselves are consistent.

Calculating the mean difference and 95% confidence intervals will provide estimate of any offset between two devices. Bland-Altman plots with limits of agreement will also provide a visual indication of the level of agreement between the two devices.

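### The Bland-Altman limits are not related to gestational age, although the acceptable difference is; if the spread of differences grows with gestation, one set of mm limits would mislead at both ends

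*Protocol*

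**What the plan says.** Section 5.2 of the protocol, exploratory outcome 3, takes high Bland-Altman agreement on fetal biometry to be "defined as ≥95% of the differences between the two measurement methods" that "fall within the clinically acceptable range of ±3 to ±7 mm, depending on gestational age". The tolerance is therefore gestation-specific. No table links gestation to tolerance, and HC, AC and FL are not separated.

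Section 10.1 names Bland-Altman limits of agreement as the method for the agreement outcomes. On numbers it says "We will aim to include 60 patients per cohort" and "The overall assessment of the devices from the combined three groups will involve a total sample of 180 paired scans".

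Section 10.2 adds "Calculating the mean difference and 95% confidence intervals will provide estimate of any offset between two devices" and "Bland-Altman plots with limits of agreement will also provide a visual indication of the level of agreement between the two devices". The only grouping that it names is the cohort, for the ICC and Spearman analyses. It mentions no regression on gestation or fetal size, no percentage or log scale and no gestational strata.

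The exploratory objectives concern "hand-held POCUS for the assessment of second and third trimester fetal biometry", so the gestational span is wide. Section 6 and Appendix 1 record gestation for every participant.

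**The concern.** Ordinary limits of agreement (mean difference ± 1.96 SD) describe 95% of differences at every gestation only if the mean and spread of the differences are the same throughout. The protocol treats the acceptable mm difference as dependent on gestation, yet its analysis text gives limits and an offset with no reference to gestation. A limit that does not vary is hard to read against a tolerance that does.

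If the spread grows as pregnancy advances, single limits would understate disagreement between the devices late and overstate it early. They would also move with the gestational mix. The three cohorts could then show different limits without any difference in device performance, which bears on exploratory objective 2 (validity by risk group).

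**Working it through.** **The plan's own figures.** 3 cohorts × 60 = 180 patients and 2 × 180 = 360 scans, which agrees with "the total number of patients will be 180, and the number of scans performed 360". The protocol gives no SD of differences and no expected limits, so there is no figure for the limits to reproduce.

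**Inputs.** From section 5.2: tolerance ±3 to ±7 mm and a required share of 95%. Assumed, because the documents do not say: the tolerance rises with gestation, there is no bias at any gestation, differences are normal, participants are spread evenly over the range, and the true 95% range at each gestation runs in a straight line from ±a (earliest) to ±b (latest).

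**Pooled limit.** The SD at a given point is t/1.96, with t uniform between a and b. The pooled limit is L = 1.96 × √(mean of SD²) = √[(b³ − a³) / (3(b − a))].

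For a = 3 and b = 7: L = √[(343 − 27)/12] = √26.33 = 5.13 mm.

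- Early end: 5.13/3 = 1.71, so 71% too wide. Share outside = 2 × [1 − Φ(1.96 × 5.13/3)] = 2 × [1 − Φ(3.35)] = 0.08%.
- Late end: 5.13/7 = 0.73, so 27% too narrow. Share outside = 2 × [1 − Φ(1.96 × 5.13/7)] = 2 × [1 − Φ(1.44)] = 15.1%.
- Over the latest third of the range 11.3% fall outside, and over the whole range 5.5%. The overall figure looks nearly right while both ends are wrong.

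**Range over other assumptions** (nominal share outside: 5%).

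| True 95% range, mix of gestations | Pooled limit | Outside, early end | Outside, late end |
|---|---|---|---|
| ±3 to ±7 mm, even | ±5.13 mm | 0.1% | 15.1% |
| ±3 to ±7 mm, more early scans | ±4.4 mm | 0.4% | 21.4% |
| ±3 to ±7 mm, more late scans | ±5.7 mm | under 0.1% | 10.8% |
| ±4 to ±6 mm, even | ±5.03 mm | 1.4% | 10.0% |
| ±3 to ±5 mm, even | ±4.0 mm | 0.8% | 11.3% |
| Constant spread | correct | 5% | 5% |

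The first three rows differ only in who is scanned when, and the limit moves between ±4.4 and ±5.7 mm. In each of those rows every gestation has exactly 95% of differences within its own tolerance, so outcome 3 is met exactly. The outcome 3 count is not disturbed by what happens to the pooled limits.

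**Would gestation-specific limits do better?** In simulation the absolute residuals were regressed on gestation and the fitted value was scaled by √(π/2) × 1.96. Root mean square error of the late-end limit:

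| True 95% range | n | Pooled | Regression |
|---|---|---|---|
| ±3 to ±7 mm | 180 | 1.90 mm | 0.69 mm |
| ±4 to ±6 mm | 180 | 1.01 mm | 0.62 mm |
| ±3 to ±7 mm | 60 | 1.97 mm | 1.18 mm |
| ±4 to ±6 mm | 60 | 1.09 mm | 1.09 mm |
| ±4.5 to ±5.5 mm | 60 | 0.70 mm | 1.05 mm |
| Constant | 60 | 0.45 mm | 0.99 mm |

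On 180 pairs the regression limits gain under both trends shown. On 60 pairs they gain only under the strong trend and lose when the spread is nearly constant.

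**The case against.** The strongest reply is that a clinical tolerance is not a measure of spread. The ±3 to ±7 mm range says how much error is acceptable at a given gestation, not how much the devices differ. The documents give no SD of differences, so the trend in the calculation is assumed. A reader might infer that the protocol's criterion shows pooled limits to be wrong; it does not. This part of the reply stands in full, and it makes the point conditional. Even the direction, wider later, is read from the order of the two figures.

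Second, the protocol never says that one set of limits covers all gestations, and a separate SAP could specify otherwise. That also stands. The inference rests on the combined analysis and on the cohort being the only grouping named. Against this, section 10.2 has its own sub-heading for the statistical analysis plan and fixes the agreement methods there.

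Third, no decision rests on the limits. The formal criterion counts differences against a gestation-specific tolerance, and section 10.2 gives the plot a visual role. This stands. A Bland-Altman plot against fetal size would probably reveal a fan shape, but the text does not say what would follow from one.

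Fourth, a reader might infer that misleading limits would pass into the sample size of the later trial. Exploratory outcome 6 says only that study data will supply variability estimates; it does not say that these come from the limits of agreement. Nor would gestation-specific limits alter the sample size argument in section 10.1.

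**Conclusion.** The point holds as a conditional one. The protocol makes acceptable disagreement depend on gestation but plans limits and an offset that, as far as the text shows, do not. If the spread of differences follows the tolerance, single limits of about ±5.1 mm would leave out 0.1% of differences at the early end and 15.1% at the late end, against a nominal 5%. With a milder trend of ±4 to ±6 mm the late-end figure is 10.0%. If the mean and spread of the differences are constant, the pooled limits are correct.

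These figures assume no bias, normal differences, an even spread of gestations and a linear change. They illustrate the possible size and do not predict what the data will show. The stakes are moderate: the outcome is exploratory and the ≥95% criterion is untouched. The change is still worth making because it is nearly free, and because fixing the rule now avoids choosing the form of the limits after seeing the plot.

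**What to change.** Add to section 10.2, for each of HC, AC and FL in the combined 180 pairs:

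- Regress the POCUS-SUM difference on gestational age at scan, then regress the absolute residuals on gestational age, and report both trends.
- If either shows a trend, report regression-based limits (fitted mean difference ± 1.96 × fitted SD) at stated gestations, or limits on the percentage (log-ratio) difference, alongside the pooled mm limits.
- If neither shows a trend, keep the pooled mm limits.
- Treat any gestation-specific limits within a cohort of 60 as descriptive.

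The cost is a few lines of text and a little extra analysis, with no new data. The downside is precision at the ends of the gestational range. Under the ±3 to ±7 mm illustration, the SD of the estimated late-end limit is about 0.7 mm with 180 pairs and 1.2 mm with 60. For the pooled limit it is about 0.3 and 0.5 mm, but that limit is then biased.

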#### Data anonymisation

Patient confidentiality will be maintained by assigning a unique personal identification number to replace any identifiable patient data when sharing study data. For instance, when a new patient is added to the study, they will be assigned a partipant ID number. By utilising such identification numbers, the confidentiality of study data is preserved.

In this trial, we will manage four distinct data packages, each with specific storage and security protocols to ensure patient confidentiality and data integrity.

Package 1: Consent Forms

Package 1 consists of signed consent forms, which contain identifiable information, including the participant's name, date of birth, hospital number, NHS number, signature, and Trial ID. These forms will be stored in a locked filling cabinet within the University department at Liverpool Women's Hospital. This will be accessible

only to the Study Steering Group (SSG). The secure storage ensures that participant identity is protected, and access is strictly controlled.

Package 2: Clinical Data

Package 2 consists of clinical data, including numerical measurements and descriptive information derived from the ultrasound scans. These data will be anonymized, with each dataset associated only with the participant's Trial ID. The Trial ID will serve as a unique identifier. Package 2 will be recorded in REDCap, a secure electronic data capture system, which will effectively separate the identifiable information (from Package 1) from the clinical data (in Package 2). This separation minimizes the risk of re-linking the datasets, thereby enhancing participant privacy and ensuring compliance with data protection regulations. Following completion of data collection, the pseudonymised data will be downloaded from REDCap in CSV format and analysed in SPSS.

Package 3: POCUS ultrasound images

Package 3 consists of POCUS ultrasound images obtained for the sole purpose of the study. These are obtained on the device and will be stored on the University Active Data Store in files coded by their personal identification number only. These files will be encrypted and deleted at the closure of the study.

Package 4: Questionnaire responses

Package 4 consists of questionnaire responses generated from REDCap in a CSV file. The responses will be linked to data from Packages 1, 2, and 3 by their participant number. The questionnaire will only be offered to RUFUS-AFI study participants.

Together, these packages of data will be securely managed to maintain participant confidentiality and to facilitate accurate and efficient data analysis.

At the end of the data collection period, only the pseudonymised data obtained via the REDCAP will be transferred to a comma-separated values (CSV) file and downloaded for statistical analysis. The REDCAP will then be closed, and the data archived for at least 10 years following closure of the study.

All research data will be stored within University of Liverpool data storage infrastructure and will comply with the research data management policy researchdatamanagementpolicy.pdf (liverpool.ac.uk) All data will be password protected and accessible by the necessary members of the research team only. Data which will be

used for subsequent analysis will undergo full anonymisation by decoupling of the identifiers from the data. On completion of the study, all study data including consent forms and other participant identifiable information will be stored for a minimum of 10 years. The University of Liverpool Active DataStore provides a centralised, secure, supported data storage facility for electronic data, with ongoing access for the life span of a project. This space, and its underlying technical infrastructure are fully supported by IT Services who continually review and improve security arrangements. The Active DataStore has many layers of protection, with data replicated between two secure physical locations and backed up regularly. Additionally, a regular tape backup is made to a third physical location, and segregated from the public network both physically and logically. The research data will be accessed only by named members of the research team gr anted password protected access to the Active DataStore by the Chief Investigator.

#### 11.REGULATORY ISSUES

### 11.1 Ethics Approval

Before the start of the study, a favourable opinion will be sought from the UK Health Departments Research Ethics Service NHS REC for the study protocol, informed consent forms and other relevant documents e.g. advertisements. Health Research Authority (HRA) approval will be obtained where required.

The study will be submitted to Liverpool Women's Hospital for Confirmation of Capacity and Capability. The study will be conducted in accordance with the recommendations for physicians involved in research on human subjects adopted by the 18th World Medical Assembly, Helsinki 1964 and later revisions.

# 11.2 Confidentiality

The Chief Investigator will preserve the confidentiality of participants taking part in the study and will abide by the Data Protection Act 2018 and the UK GDPR as amended from time to time and any successor legislation in the UK and any other directly applicable regulation relating to data protection and privacy.

An electronic copy of all consent forms will be saved to the University of Liverpool Active Data Store. This folder will be password protected and accessed only by nominated members of the core research team. It will be kept separate from all other study related information and data. Coded, de-personalised data will be stored on the REDCAP database during data collection. At the end of the data collection period, anonymised data obtained and stored in the REDCAP will be transferred to a comma-separated values (CSV) file and

downloaded for statistical analysis. The REDCAP will then be closed, and the data archived for a minimum of 10 years following closure of the study.

# 11.3 Indemnity

The University of Liverpool holds Indemnity and insurance cover with Newline Insurance Company, which apply to this study.

#### 11.4 Audits

The study may be subject to inspection and audit by the University of Liverpool under their remit as sponsor and other regulatory bodies to ensure adherence to GCP and the UK Policy Framework for Health and Social Care Research (v3.2 10th October 2017).

# 11.5 Independent Oversight

This study will not convene neither a Steering Committee nor an Independent Safety and Data Monitoring Committee (ISDMC) as this is a low-risk non-interventional study. Oversight will be provided by the study steering group and the Sponsor.

The study with have a study steering group that will be able to review at regular intervals all accumulating data, with the responsibility of reviewing the recruitment of participants, the collection of all essential data and to assess participant safety. Biannual meetings of an advisory group will include all members of the study steering group as well as two independent advisors (Profs [name] and [name], University of Liverpool). The purpose of these independent advisors is to ensure adequate progress of the project in line with the proposed timeline, provide additional clinical experise, and to address any significant concerns pertaining to its delivery. This advisory group may suggest changes to the study.

### 12. END OF STUDY

This study will end once the data collection is complete. After the end of study is declared no study activity, other than final report writing (following 'lock' of the study database and completion of statistical analyses), will be undertaken. As there are no formal hypotheses being tested, there are no formal stopping rules (other than safety) or mechanisms defined here to stop the study prior to the planned end of study.

# 12.1 Dissemination policy

The data from this study will be owned by the University of Liverpool. The findings will be shared at national and international conferences relevant to obstetricians, midwives and paediatricians, infectous disease and public health audiences. We plan to submit the work for publication in peer reviewed journals. The funders will be acknowledged on any publication and the publication will be made open access (CC-BY) in accordance with University of Liverpool requirements.

Each participant will be asked if they would like a copy of the study findings. The protocol and final study report will be published.

If this study is prematurely discontinued (e.g., due to safety) all participants must be informed and the reason for the discontinuation should be written on the end of study form for each participant.

